14.2 Sample Size/Accrual Rate

To achieve 90% power to detect a 75% increase in median PFS (44.6 vs. 25.5 months), at the two-sided 0.05 significance level, will require 306 patients total, accrued over approximately 3.0 years (assuming an accrual rate of approximately 9 patients/month), with an additional 12 months of follow-up subsequent to termination of accrual.

When the sample size in each group is 153 patients, with a total number of PFS events required of 133, an exponential maximum likelihood test of equality of survival curves with a 0.05 two-sided significance level will have 90% power to detect the difference between an Arm A (Rd) median PFS of 25.5 months and an Arm B (BiRd) median PFS of 44.6 months (a constant hazard ratio of 1.75); this assumes an accrual period of 3.0 years, a maximum follow-up time of 4.0 years, and no dropouts. The exponential assumption is for planning purposes only, actual analysis will employ nonparametric methods for estimation and testing of survival distributions. Assuming a 10% dropout rate, approximately 337 patients will be accrued to the study.

A futility analysis will be conducted after 50% of the total PFS events required for final analysis has occurred (i.e., 66 of the 133 required PFS events). No accrual suspension is required to conduct the futility analysis. If at this point (i.e., after accumulation of 66 PFS events) the hazard ratio of the control arm over the experimental arm is 1.0 or less, the study will be stopped for futility.

14.3 Analysis of Progression-Free Survival

Because the analysis of PFS can be difficult, especially in the presence of missing data and lost-to-follow-up, sensitivity analyses can be helpful in determining whether the PFS analysis is robust. As suggested by the alternative PFS definitions recommended in the FDA's Guidance for Industry, "Clinical Trial Endpoints for the Approval of Cancer Drugs and Biologics (May, 2007), the following three types of PFS analyses will be

conducted:

Table A. PFS #1 (includes documented progression only) (Primary PFS Analysis):

Situation	Date of Progression or Censoring	Outcome
No baseline tumor assessments	Randomization	Censored
Progression documented between scheduled visits	Earliest of: 
 • Date of hematological assessment showing progression; or • Date of radiological assessment showing progression; or • Date of urine assessment showing progression 	Progressed
No progression	Date of last hematological, radiological, or urine assessment	Censored
Treatment discontinuation for undocumented progression	Date of last hematological, radiological, or urine assessment	Censored
Treatment discontinuation for toxicity or other reason	Date of last hematological, radiological, or urine assessment	Censored
New anticancer treatment started	Date of last hematological, radiological, or urine assessment	Censored
Death before first PD assessment	Date of death	Progressed
Death between adequate assessment visits	Date of death	Progressed
Death or progression after more than one missed visit	If progression: 
 • Date of hematological assessment showing progression; or • Date of radiological assessment showing progression; or • Date of urine assessment showing progression OR, if not progression: Date of last hematological, radiological, or urine assessment	Censored

Table A represents the primary PFS analysis that only includes well-documented and verifiable progression events. Other data are censored. In Table A, the progression dates are 1) based only on radiological assessments verified by an IRC (clinical progression will not be considered a progression endpoint), 2) assigned to the first time when disease progression is noted, and 3) the date of death when the patient is closely followed. However, deaths occurring after two or missed visits will be censored at the last visit.

Table B. PFS #2 (uniform progression and assessment dates) (PFS Sensitivity Analysis #1):

Situation	Date of Progression or Censoring	Outcome
No baseline tumor assessments	Randomization	Censored
Progression documented between scheduled visits	Date of next scheduled visit	Progressed
No progression	Date of last visit with adequate assessment	Censored
Treatment discontinuation for undocumented progression	Date of last visit with adequate assessment	Censored
Treatment discontinuation for toxicity or other reason	Date of last visit with adequate assessment	Censored
New anticancer treatment started	Date of last visit with adequate assessment	Censored
Death before first PD assessment	Date of death	Progressed
Death between adequate assessment visits	Date of death	Progressed
Death or progression after more than one missed visit	Date of last visit with adequate assessment	Censored

Table B presents a sensitivity analysis for PFS that helps to correct for potential bias in follow-up schedules for tumor assessment by assigning the dates of censoring and events only at scheduled visit dates. This approach can introduce bias if the progression occurred closer to the last visit, particularly in an open-label study.

Table C. PFS #3 (includes investigator claims) (PFS Sensitivity Analysis #2):

Situation	Date of Progression or Censoring	Outcome
No baseline assessment	Randomization	Censored
Progression documented between scheduled visits	Next scheduled visit	Progressed
No progression	Date of last visit with adequate assessment	Censored
Investigator claim of clinical progression	Scheduled visit (or next scheduled visit if between visits)	Progressed
Treatment discontinuation for toxicity or other reason	Date of last visit with adequate assessment	Censored
New anticancer treatment started with no claim of progression	Date of last visit with adequate assessment	Censored
Death before first PD assessment	Date of death	Progressed
Death between adequate assessment visits or after patient misses one assessment visit	Date of death	Progressed
Death after an extended lost-to-follow-up time (two or more missed assessments)	Last visit with adequate assessment	Censored

Table C presents a sensitivity analysis for PFS that evaluates PFS according to the investigator's assessment. This approach can introduce bias if the progression occurred closer to the last visit, particularly in an open-label study.

Although the above PFS analyses will initially censor patients who died or progressed after more than one missed visit (Tables A/B/C), these analyses will also be redone to classify the patients as progression events, and the date of death will be used as the date of progression. Counting such deaths as progression events may overestimate PFS, but also minimizes bias.

Lastly, a comparison of the adequacy of follow-up and the number of scheduled assessments in each treatment arm will be performed to evaluate potential bias resulting from missing data. Because the trial is unblinded, there is always the potential for bias (i.e., evaluation-time bias) between the treatment arms because of the subjective aspects of the progression endpoint. To evaluate the impact of any evaluation-time bias in the assessment of PFS, we will use the approach of Freidlin and Korn when comparing PFS between the two treatment arms (Freidlin B, Korn EL, Hunsberger S, Gray R, Saxman S, Zujewski J. Proposal for the use of progression-free survival in unblinded randomized trials. *Journal of Clinical Oncology*. 2007;25:2122-2126). The method of Freidlin and Korn will not be the primary analysis. The primary analysis will be performed as discussed in section 14.2, first two paragraphs. The Freidlin/Korn method will be performed to assess the extent of any evaluation-time bias that may have resulted from comparison of the two treatment arms in the primary analysis (i.e., primary analysis using the actual reported progression times; progression-free survival curves).

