1.3 Schedule of Assessments

Procedure	Screening <28 days prior to start date (unless otherwise indicated)	Cycle 1 Day 1	Cycle 1 Days 8, 15, 22	All Other Cycles Day 1	End of Study ⁹	Follow- Up Phase (Every 6 months)
Complete medical history with quality of life assessment.	X	X		X		
Physical exam, KPS, vital signs, height and weight	X	X		X		
CBC with differential	X	X	X	X	X	
Complete metabolic profile ^{1,2}	X	X	X	X ²	X	
Generate / review new drug diary		X		X		
Collect / review prior drug diary				X	X	
SPEP, IF, quantitative immunoglobulins ³	X	X		X	X	
Serum free light chains ³	X	X		X	X	
24-hour urine for UTP, UPEP, UIF ³	X	X		X	X	
β ₂ M ³	X					
CRP	X					
Urinalysis	X					
Pregnancy test ⁴	X	X		X	X	
Register patient into RevAssist [®] program ⁵	X					
Skeletal survey, MRI, or whole body PET/CT scan	X ⁶			X ⁸	X ⁸	
Bone marrow biopsy and aspirate ⁷	X ⁶			X ⁸	X ⁸	
Concurrent medication use survey	X	X		X		
Electrocardiogram	X					
Drug dispensation ⁶				Continuous		
Adverse event				Continuous		

monitoring						
Obtain Follow-Up anti-cancer treatments						X
Obtain disease status, physical status, survival information, and if any occurrence of secondary primary malignancies						X

1. Includes sodium, potassium, chloride, CO₂, calcium, blood urea nitrogen (BUN), serum creatinine and calculated creatinine clearance, glucose, albumin, total protein, alkaline phosphatase, total bilirubin, SGOT/AST, SGPT/ALT, LDH, Uric Acid. Phosphorus and magnesium are performed at screening and Cycle 1 Day 1.
2. To include Thyroid Stimulating Hormone (TSH) at screening, and every 3 months beginning with cycle 4 (more often if clinically indicated).
3. UTP = urine total protein; UPEP = urine protein electrophoresis; UIF = urine immunofixation; SPEP = serum protein electrophoresis; IF = serum immunofixation; β₂M = beta-2 microglobulin.

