10.4 Post Study Follow-up

All attempts will be made to follow patients until progression or death. Subjects who have been discontinued from study will still be followed in a clinic setting to the fullest extent possible on a monthly to bi-monthly basis. Those who choose not to resume regular clinic follow-up will be contacted every 6 months by telephone or electronically

to collect post study information. The post-study collection information will consist of a telephone interview between the clinical investigator and the discontinued patient. The information requested will be current disease status including information about the development of secondary primary malignancies, current treatment use, and physical status of the patient.

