14.0 STATISTICAL CONSIDERATIONS

14.1 Study Design/Primary Endpoint

The study is a randomized phase III design, and the primary endpoint in both treatment arms is median PFS. PFS will be defined as the time from randomization day until objective progression or death from any cause. The PFS distributions of the two treatment arms will be estimated by Kaplan-Meier survival analysis and the PFS distributions will be compared by an unstratified log-rank test. Ninety-five percent confidence intervals for the Kaplan-Meier PFS estimates will be calculated using

Greenwood's formulae. The primary comparison will be made using the intent-to-treat (ITT) patient population. Patients will be analyzed based on their randomization assignments, regardless of therapy initiation or compliance. A secondary analysis will be performed comparing "evaluable" patients as patients who met eligibility requirements, have initiated therapy, and were not removed from the study for non-compliance or patient withdrawal.

The median PFS for MM patients receiving Revlimid /dexamethasone chemotherapy (Rd) (Arm A) is expected to be approximately 25.5 months, as reported in the MM-010 study of continuous Rd vs Rd for 18 months (Facon T, Dimopoulos M, Dispenzieri A, et al: Initial phase 3 results of the FIRST trial in newly diagnosed multiple myeloma patients ineligible for stem cell transplant. 2013 ASH Annual Meeting. Abstract 2. Presented December 8, 2013.). Therefore, the target median PFS for patients receiving Revlimid/dexamethasone/Clarithromycin (BiRd) (Arm B) is hypothesized to be 44.6 months (target hazard ratio = 1.75).

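### All three PFS tables censor patients who stop treatment for toxicity or other reasons, against the PFS definition in 14.1, and post-treatment follow-up names no myeloma tests

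*Combined protocol and SAP*

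**What the plan says.** Section 14.1 makes PFS the primary endpoint, with progression or death from any cause as the event. It takes the intent-to-treat population for the primary comparison: "Patients will be analyzed based on their randomization assignments, regardless of therapy initiation or compliance".

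Section 14.3 (Analysis of Progression-Free Survival) turns this into rules.

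- **Discontinuation row.** In Table A, the primary analysis, "Treatment discontinuation for toxicity or other reason" has the outcome Censored, dated at the last hematological, radiological or urine assessment. Tables B and C have the same row, censored at the last adequate visit.
- **Death rows.** All three tables count a death before the first progression assessment, or between adequate assessment visits, as an event. None of them ranks these rows against the discontinuation row.
- **Re-run.** The paragraph after Table C repeats the analyses with deaths or progressions after more than one missed visit counted as events.

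On data collection, the schedule in 1.3 has serum and urine protein studies and free light chains on day 1 of each cycle and at End of Study. The six-monthly Follow-Up column asks only for later anticancer treatments and to "Obtain disease status, physical status, survival information, and if any occurrence of secondary primary malignancies". Section 10.4 is more ambitious: "All attempts will be made to follow patients until progression or death". It foresees monthly to bi-monthly clinic visits where possible, with six-monthly remote contact for patients who do not return. Section 4.1 also plans long-term follow-up for disease status and survival.

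**The concern.** Take a patient who stops in cycle 5 for toxicity and has a confirmed M-protein rise, or dies, four months later. Under 14.1 this is an event. Under the discontinuation row the patient is censored at the last assessment. The death row could give the opposite answer for the death, and nothing says which row wins. Two analysts could build different primary datasets from the same records.

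If the discontinuation row wins, the primary analysis estimates PFS while on treatment. Stopping for toxicity is likely to be related to prognosis and may differ between arms of an open-label trial in which one arm adds a drug. Censoring at that moment is then informative. Because Tables B and C carry the same row, the planned sensitivity tables cannot show whether it matters.

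The schedule adds a practical problem. Even if the rule is corrected, a progression after stopping must be documented by a test, and the Follow-Up column lists none.

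**Working it through.** **Inputs from 14.2.** Medians are 25.5 (Rd) and 44.6 months (BiRd), with "a constant hazard ratio of 1.75". The test is "at the two-sided 0.05 significance level" with 90% power. There are 153 patients per arm and 133 required events, with 36 months of accrual, a maximum of 48 months and no dropouts. Inflated enrolment is about 337.

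**The plan's figure.** Events = 4(1.960 + 1.282)² / (ln 1.75)² = 134.2, so 135 against the stated 133. Power with d events is Φ(½√d · ln 1.75 − 1.96), which gives 89.7% at d = 133. The plan's figure reproduces.

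**Expected events if nobody is censored for stopping.** The hazards are ln 2/25.5 = 0.02718 and ln 2/44.6 = 0.01554 per month. With uniform entry u over 0 to 36 months, the event probability is the average of 1 − exp[−λ(48 − u)]. This is 0.540 for Rd and 0.364 for BiRd. Events = 153 × (0.5397 + 0.3644) = 138.

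**Expected events under the literal row.** The documents give no rate of stopping without progression, so it is assumed here. For 20% per arm by 24 months, γ = −ln(0.80)/24 = 0.00930 per month. The event probability becomes λ/(λ+γ) times the average of 1 − exp[−(λ+γ)(48 − u)], which is 0.477 and 0.319.

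- 306 patients: 153 × (0.4774 + 0.3187) = 122 events, power about 87%.
- 337 patients: 168.5 × (0.4774 + 0.3187) = 134 events, power about 90%.

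The range of assumed rates, same method, constant stopping hazard, equal in both arms:

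| Stopped by 12 months | Events at month 48, N = 306 | Power, N = 306 | Events at month 48, N = 337 |
|---|---|---|---|
| 5% | 130 | 89% | 144 |
| 10% | 123 | 87% | 135 |
| 15% | 115 | 85% | 127 |
| 20% | 108 | 83% | 119 |
| 30% | 95 | 78% | 105 |

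Ten percent by 12 months is 1 − 0.9² = 19% by 24 months, so the second line is close to the worked case. At that rate 306 patients reach 133 events at about month 52.5, so waiting recovers them. At 30% by 12 months, 306 patients cannot yield more than about 126.

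**Bias (simulation, 153 per arm, same accrual, all stopping inputs assumed).** On-treatment hazards are equal in the two arms, and the hazard is multiplied after stopping. Ratios are BiRd:Rd.

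| Stopped by 24 months, Rd / BiRd | Hazard after stopping | Full follow-up | Censored at stop |
|---|---|---|---|
| 20% / 30% | ×1.5 | 1.03 | 1.00 |
| 20% / 40% | ×2 | 1.10 | 1.00 |

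The 1.00 follows from the set-up: censoring at the stop leaves only the on-treatment hazards, which were made equal. A harsher assumption (10% against 30% stopped by 12 months, hazard doubled) gives 1.15 against 1.00. With the planned medians and that same assumption, it gives 0.67 against 0.58.

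**The case against.** The strongest reply is that the plan has more safeguards than the discontinuation row suggests.

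- **A reader might infer that deaths after stopping are lost.** The documents do not establish this. The death rows have no on-treatment limit, survival is followed, and no row is given precedence. What is shown is a missing rule.
- **A reader might infer that no planned analysis counts later events.** That is too strong. The re-run can recover some of them, Table C accepts investigator claims of clinical progression, overall survival is compared by log-rank, and descriptive event-free survival counts leaving the protocol for any reason. But the re-run is triggered by missed visits rather than by stopping, and it dates events at death, so a progression without death has no date. None of these corrects the primary analysis.
- **A reader might infer a breach of intent-to-treat.** Censoring removes nobody from the randomised population. The sharper conflict is with the definition of PFS.
- **A reader might infer that follow-up ends with treatment.** Sections 4.1 and 10.4 say otherwise, and PFS2 needs later disease tracking. The gap is that no tests are named.
- **A reader might infer that 133 events cannot be reached.** With 20% stopping by 24 months, the 337 patients of 14.2 give about 134. Section 4.1 caps enrolment at 306, a separate inconsistency.

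Two further replies carry some weight. The BiRd modification table adds only one off-study row, and 4.1 continues the remaining drugs when one is stopped, so a large difference in stopping is not a given. The plan also says its tables follow alternative definitions suggested in regulatory guidance. That explains where they came from, but it does not reconcile them with 14.1.

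**Conclusion.** The point holds in this form. All three tables censor at discontinuation for toxicity or other reason, 14.1 counts progression or any death, and nothing decides between them. Section 14.3 refers the primary analysis back to 14.2, which has no event rules. Read literally, the primary result is PFS on treatment, and neither sensitivity table tests it. Documented progression after stopping is intended but not assured.

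The size depends on stopping rates that the documents do not give. At 20% per arm by 24 months, the cost at month 48 is about 16 of 138 events with 306 patients. The distortion of the hazard ratio is modest in the main scenarios (1.03 to 1.10 shown as 1.00) and needs both unequal stopping and a higher hazard afterwards. A reader might infer that the rule would manufacture a benefit for BiRd. These scenarios show a disadvantage hidden, not a benefit created from equal arms, and the documents do not establish that BiRd patients will stop more often. The reason to act is that the primary endpoint has two incompatible rules, and assessments not collected during follow-up cannot be recovered later.

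**What to change.** In 14.3, Table A:

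1. State that documented progression, or death from any cause, after discontinuation for toxicity or other reason is an event in the primary analysis, and that this takes precedence over the discontinuation row.
2. Keep the present censoring row as a named sensitivity analysis.
3. State how the row for new anticancer treatment ranks against these events. Otherwise patients who stop and then start another therapy stay ambiguous.

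In 1.3 and 10.4, reconcile the Follow-Up column with the clinic visits that 10.4 already intends, so that serum and urine M-protein and free light chain results are recorded until progression for patients who stopped before it.

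The cost is a few lines of analysis wording, one column of the schedule, and some blood and urine tests in patients off treatment. The effect estimate will include time off the assigned drugs, which is what 14.1 already describes.

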MRD: Minimal residual disease testing will be performed in subjects who achieve complete response. MRD testing may be performed either by flow cytometry or PCR, whichever is more readily available at the study institution.

Subjects will continue their randomized treatment assignment until disease progression or unacceptable toxicity (whichever occurs first). In case toxicity precludes dosing of one agent (i.e dexamethasone, clarithromycin, lenalidomide), treatment regimen will continue with the remaining agents. Subjects unable to receive ALL the components of the assigned treatment arms will be removed from study after reasonable attempts to dose reduce and manage side effects. Subjects with elevations of AST/ALT greater than three times the upper limit of normal, with concomitant elevation of bilirubin 2 times the upper limit of normal, not attributable to disease, should be discontinued from treatment. Subjects can also be removed from study at investigator's discretion, or if they withdraw consent. At completion or early discontinuation of treatment, subjects will be followed for 30 additional days or up to the initiation of subsequent treatment (whichever occurs first), after which they will be off the active treatment phase of the study. Long term follow up for disease status and survival will proceed until the subject has withdrawn consent, is lost to follow up, or has died.

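### Tables A, B and C censor PFS when treatment stops for toxicity or another reason, against the PFS definition in 14.1, and no planned PFS analysis lifts that censoring

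*Combined protocol and SAP*

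**What the plan says.** Section 14.1 gives the endpoint: "PFS will be defined as the time from randomization day until objective progression or death from any cause". The primary comparison is intention-to-treat: "Patients will be analyzed based on their randomization assignments, regardless of therapy initiation or compliance".

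Section 14.3 (Analysis of Progression-Free Survival) then sets the event and censoring rules. In Table A, the primary analysis, the row "Treatment discontinuation for toxicity or other reason" has the outcome censored, dated at the last haematological, radiological or urine assessment. Tables B and C carry the same row, also censored, dated at the last visit with adequate assessment. A separate row censors at "New anticancer treatment started" (Table C limits this to patients with no claim of progression).

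Follow-up does not end with treatment. Section 4.1: "Long term follow up for disease status and survival will proceed until the subject has withdrawn consent", or is lost to follow-up or dies. Section 10.4: "All attempts will be made to follow patients until progression or death".

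The text after Table C adds a rerun for patients who died or progressed after more than one missed visit: "these analyses will also be redone to classify the patients as progression events". It also adds a comparison of follow-up adequacy by arm and a Freidlin–Korn analysis of evaluation-time bias. Event-free survival (2.2) counts coming off protocol as an event, but 14.4 presents it descriptively only.

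**The concern.** The definition in 14.1 has two ways to end: progression or death. Stopping a drug is neither. If the Table A row means what it appears to mean, the primary test compares the arms while patients remain on treatment, and progressions and deaths after a toxicity stop are left out even though the protocol plans to observe them.

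The table also does not say which row wins. A patient who stops for toxicity and later dies between adequate assessments fits the stop row (censored) and the death row (event). Two analysts could reach different primary results from the same data.

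What is at stake is which effect the trial reports. If patients in both arms progress at a similar rate once off treatment, censoring at the stop gives a hazard ratio further from 1 than the one 14.1 describes, and no planned PFS analysis would show the difference.

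**Working it through.** **1. Which reading is natural.** Table A already has a row for patients without progression, censored at the same kind of date. If the stop row covered only patients who never progress, it would add nothing. It does work only if stopping itself triggers censoring. The row does not say *last assessment before stopping*, so this is the natural reading and not a certain one.

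**2. Does another PFS analysis lift it?**
- Tables B and C: same row, same outcome.
- Missed-visit rerun: aimed at missed visits. It might recover some stopped patients who also missed visits, but only incidentally.
- Freidlin–Korn: addresses assessment timing.
- Evaluable analysis (14.1): removes further patients.
- Event-free survival: a different endpoint, with no comparison between arms.

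None does.

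**3. The plan's own figures.** Section 14.2 gives medians of 25.5 and 44.6 months, two-sided 0.05, 90% power, 133 events, 153 per arm, 36 months of accrual and a 48-month maximum.
- Schoenfeld: 4(1.960 + 1.282)²/(ln 1.75)² gives 135 events, against 133 stated. Power at 133 events is 0.897.
- Expected events at month 48: the event probability per arm is (1/36)∫₁₂⁴⁸ (1 − e^(−λt)) dt with λ = ln 2/median. This is 0.5397 for Rd and 0.3644 for BiRd, so 153 × (0.5397 + 0.3644) = 138.3.

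The plan's arithmetic reproduces and is not in dispute.

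**4. Effect on the hazard ratio.** All stopping inputs are assumptions:
- exponential PFS at the planned medians while on treatment;
- stop hazard −ln(1 − p)/24, where p is the proportion stopped by month 24;
- after stopping, hazard 1.0 or 1.5 times control in both arms;
- new therapy starts a median of 4.5 months after stopping;
- 153 per arm, cut-off at month 48, 20,000 simulated trials per cell.

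Hazard ratios are Rd over BiRd, as in 14.1. *Row reworded* keeps patients at risk after stopping but still censors at new therapy.

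| Stops Rd / BiRd | Hazard after stop | Censor at stop | Row reworded | 14.1 definition |
|---|---|---|---|---|
| 10% / 10% | 1.0 × control | 1.756 | 1.729 | 1.686 |
| 20% / 20% | 1.0 × control | 1.758 | 1.705 | 1.624 |
| 20% / 20% | 1.5 × control | 1.753 | 1.681 | 1.595 |
| 30% / 30% | 1.0 × control | 1.751 | 1.670 | 1.557 |
| 30% / 10% | 1.0 × control | 1.751 | 1.725 | 1.683 |
| 30% / 10% | 1.5 × control | 1.751 | 1.755 | 1.759 |
| 20% / 20% | unchanged | 1.753 | 1.753 | 1.753 |

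A separate run of 2,000 trials for the second line gave BiRd/Rd ratios of 0.572 and 0.617, that is 1/0.572 = 1.75 and 1/0.617 = 1.62.

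In the second line, rewording the row recovers (1.758 − 1.705)/(1.758 − 1.624) = 0.053/0.134, about 40% of the gap. With 20% stops, both post-stop hazards and a median of 3 to 12 months to new therapy, the share runs from 30% to 69%.

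**5. Effect on events.** With the stop hazard c added, the integrand in step 3 becomes (λ/(λ + c))(1 − e^(−(λ + c)t)). For 306 patients, events at month 48 are 130, 122 or 113 at 10%, 20% or 30% stops. The 133rd event then arrives at about month 49.0, 52.5 or 58.3, against month 46.5 with no such censoring.

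**The case against.** **The tables are deliberate.** Section 14.3 presents them as following FDA-suggested alternative definitions. That shows intent, but it does not reconcile Table A with 14.1 or supply the missing analysis.

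**The reading is unsettled.** The row's date wording matches the no-progression row, and the text under Table A assigns progression to the first time it is noted. This stands: every hazard ratio above depends on censoring at the stop. An edit is needed on either reading, because the rows overlap without precedence.

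**Intention-to-treat names a population.** Table A drops nobody from it. This stands in part: the conflict rests mainly on the sentence defining PFS.

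**The model is stark.** It removes all benefit at the stop and holds the 1.75 ratio throughout treatment, although maintenance in 9.1 lists only lenalidomide and dexamethasone. Section 14.1 also states 1.75 for PFS as defined, not for time on treatment. The figures therefore size the gap between two rules; they do not predict the trial's result.

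**Other planned analyses help.** Overall survival is compared from randomisation without this censoring, and follow-up adequacy is compared by arm. Neither re-estimates PFS.

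Three stronger readings are tempting, and the documents do not support them:
- *BiRd, with three drugs, will be stopped more often.* Section 4.1 continues the regimen with the remaining agents when toxicity rules out one of them, and 9.6 makes stopping clarithromycin its last dose step. The documents give no stopping rate for either arm.
- *The trial will be underpowered.* Section 14.2 ties the final analysis to 133 events. Lost events mean longer follow-up; they do not lower power at 133 events for a given hazard ratio.
- *The words "primary analysis using the actual reported progression times" contradict Table A.* In context they contrast the primary analysis with Freidlin–Korn and say nothing about censoring.

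**Conclusion.** The point holds as a conflict between 14.1 and the tables, with no planned PFS analysis that would expose its effect. It should be settled before data are seen.

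The size is illustrative. Equal stopping of 20% by month 24, with progression at the control rate afterwards, separates the two rules by about 1.75 against 1.62. The gap grows with the stopping rate. It is nil if stopping leaves each arm's hazard unchanged, and small or absent if Rd stops more often. The documents do not say which case applies, so they do not support a claim that the primary result will be overstated. They support only that it could be, and that the plan could not show it. Confidence is medium because the censoring reading is the natural one but is not explicit.

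**What to change.** 1. In Tables A, B and C, reword the row: *Treatment discontinued for toxicity or other reason without progression: patient stays at risk; later documented progression or death is an event, dated by that table's rule; if neither, censor at last assessment.* State that the missed-visit row still applies, with its planned rerun.
2. Keep censoring at treatment stop as a labelled sensitivity analysis.
3. Add one log-rank and Kaplan–Meier sensitivity analysis on the 14.1 definition. It should count every documented progression or death regardless of treatment stop, new anticancer treatment or missed visits. It is needed because the new-treatment and missed-visit rows still depart from 14.1 after step 1.

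The cost is three table rows and two analyses, one of them the present rule relabelled. It uses data already planned in 4.1 and 10.4, with no extra patients, visits or tests.

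There are two downsides. Progressions after stopping may be less well documented: the follow-up column in 1.3 lists no laboratory tests or imaging, and 10.4 allows six-monthly remote contact for patients who leave clinic follow-up. That limits how many Table A can accept. Power may also fall if benefit is lost after stopping. At 20% stops in each arm and a month-48 cut-off, the simulation gives 84–85% with the reworded row and 80–82% on the 14.1 definition, against 86–87% with censoring at the stop. That fall reflects a smaller effect under the definition the protocol states.
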